10.1.6. Data Quality Assurance

- All participant data relating to the study will be recorded on printed or electronic CRF unless transmitted to the sponsor or designee electronically (eg, laboratory data). The investigator is responsible for verifying that data entries are accurate and correct by physically or electronically signing the CRF.
- The investigator must maintain accurate documentation (source data) that supports the information entered in the CRF.
- The investigator must ensure that the CRFs are securely stored at the study site in encrypted electronic and/or paper form and are password protected or secured in a locked room to prevent access by unauthorized third parties.
- The investigator must permit study-related monitoring, audits, IRB/IEC review, and regulatory agency inspections and provide direct access to source data documents. This verification may also occur after study completion. It is important that the investigator(s) and their relevant personnel are available during the monitoring visits and possible audits or inspections and that sufficient time is devoted to the process.
- Monitoring details describing strategy (eg, risk-based initiatives in operations and quality such as Risk Management and Mitigation Strategies and Analytical Risk-Based Monitoring), methods, responsibilities and requirements, including handling of noncompliance issues and monitoring techniques (central, remote, or on-site monitoring) are provided in the Monitoring Plan.
- The sponsor or designee is responsible for the data management of this study including quality checking of the data.
- Study monitors will perform ongoing source data verification to confirm that data entered into the CRF by authorized site personnel are accurate, complete, and verifiable from source documents; that the safety and rights of participants are being protected; and that the study is being conducted in accordance with the currently approved protocol and any other study agreements, ICH GCP, and all applicable regulatory requirements.
- Records and documents, including signed ICFs, pertaining to the conduct of this study must be retained by the investigator for 15 years after study completion unless local regulations or institutional policies require a longer retention period. No

records may be destroyed during the retention period without the written approval of the sponsor. No records may be transferred to another location or party without written notification to the sponsor. The investigator must ensure that the records continue to be stored securely for so long as they are maintained.

- When participant data are to be deleted, the investigator will ensure that all copies of such data are promptly and irrevocably deleted from all systems.
- The investigator(s) will notify sponsor or its agents immediately of any regulatory inspection notification in relation to the study. Furthermore, the investigator will cooperate with sponsor or its agents to prepare the investigator site for the inspection and will allow sponsor or its agent, whenever feasible, to be present during the inspection. The investigator site and investigator will promptly resolve any discrepancies that are identified between the study data and the participant's medical records. The investigator will promptly provide copies of the inspection findings to sponsor or its agent. Before response submission to the regulatory authorities, the investigator will provide sponsor or its agents with an opportunity to review and comment on responses to any such findings.

10.1.7. Source Documents

- Source documents provide evidence for the existence of the participant and substantiate the integrity of the data collected. Source documents are filed at the investigator's site.
- Data reported on the CRF or entered in the CRF that are transcribed from source documents must be consistent with the source documents or the discrepancies must be explained. The investigator may need to request previous medical records or transfer records, depending on the study. Also, current medical records must be available.
- Definition of what constitutes source data can be found in the Monitoring Plan.

10.1.8. Study and Site Closure

The sponsor designee reserves the right to close the study site or terminate the study at any time for any reason at the sole discretion of the sponsor. Study sites will be closed upon study completion. A study site is considered closed when all required documents and study supplies have been collected and a study-site closure visit has been performed.

The investigator may initiate study-site closure at any time upon notification to the clinical research organization if requested to do so by the responsible IRB/IEC or if such termination is required to protect the health of Study Participants.

Reasons for the early closure of a study site by the sponsor may include but are not limited to:

- Failure of the investigator to comply with the protocol, the requirements of the IRB/IEC or local health authorities, the sponsor's procedures, or GCP guidelines
- Inadequate recruitment of participants by the investigator
- Discontinuation of further study intervention development

Study termination is also provided for in the clinical study agreement. If there is any conflict between the contract and this protocol the contract will control as to termination rights.

10.1.9. Publication Policy

- The results of this study may be published or presented at scientific meetings by the Investigator after publication of the overall study results or one year after end of the study (or study termination), whichever comes first.
- The investigator agrees to refer to the primary publication in any subsequent publications such as secondary manuscripts, and submit all manuscripts or abstracts to the sponsor 30 days before submission. This allows the sponsor to protect proprietary information and to provide comments and the Investigator will, on request, remove any previously undisclosed confidential information before disclosure, except for any study- or Pfizer intervention-related information necessary to the appropriate scientific presentation or understanding of the study results.
- For all publications relating to the study, the Investigator will comply with recognized ethical standards concerning publications and authorship, including those established by the International Committee of Medical Journal Editors.
- The sponsor will comply with the requirements for publication of the overall study results covering all Investigator sites. In accordance with standard editorial and ethical practice, the sponsor will support publication of multicenter studies only in their entirety and not as individual site data. In this case, a coordinating investigator will be designated by mutual agreement.
- Authorship of publications for the overall study results will be determined by mutual agreement and in line with International Committee of Medical Journal Editors authorship requirements.
- If publication is addressed in the clinical study agreement, the publication policy set out in this section will not apply.

10.1.10. Sponsor's Qualified Medical Personnel

The contact information for the sponsor's appropriately qualified medical personnel for the study is documented in the study contact list located in the supporting study documentation.

To facilitate access to appropriately qualified medical personnel on study-related medical questions or problems, participants are provided with a contact card. The contact card contains, at a minimum, protocol and IP identifiers, participant study numbers, contact information for the investigator site, and contact details for a contact center in the event that the investigator site staff cannot be reached to provide advice on a medical question or problem originating from another healthcare professional not involved in the participant's participation in the study. The contact number can also be used by investigator staff if they are seeking advice on medical questions or problems; however, it should be used only in the event that the established communication pathways between the investigator site and the study team are not available. It is therefore intended to augment, but not replace, the established communication pathways between the investigator site and the study team for advice on medical questions or problems that may arise during the study. For sites other than a Pfizer Clinical Research Unit, the contact number is not intended for use by the participant directly, and if a participant calls that number, he or she will be directed back to the investigator site.

10.2. Appendix 2: Clinical Laboratory Tests

The tests detailed in Table 7 will be performed by a central laboratory. Urine pregnancy test will be performed at the site, with test kits provided by the central laboratory.

- Local laboratory results can be used for medical decision making if the central laboratory results are not available in time. The local laboratory reports must be kept in source documents and made available for medical review as required. It is important that the sample for central analysis is obtained at the same time.
- Protocol-specific requirements for inclusion or exclusion of participants are detailed in Section 5 of the protocol.
- Additional tests may be performed at any time during the study as determined necessary by the investigator or required by local regulations.
- Pregnancy Testing
 - Refer to Section 5.1 Inclusion Criteria for screening pregnancy criteria.

Table 7. Protocol-Required Safety Laboratory Assessments

Laboratory Assessments	Parameters	
Hematology	Platelet Count Red blood cell (RBC) Count Hemoglobin Hematocrit	White blood cell (WBC) count (% and absolute: Neutrophils Lymphocytes Monocytes Eosinophils Basophils
Clinical Chemistry	Albumin Alanine Aminotransferase (ALT) Aspartate Aminotransferase (AST) Sodium Glucose (non-fasting)	Blood urea nitrogen (BUN) Potassium Alkaline phosphatase Total bilirubin Total Protein Calcium Creatinine Chloride Bicarbonate or total CO ₂
	Note: During the study, if any ALT, AST, total bilirubin, or creatinine value is ≥30% higher than the baseline value at screening, a repeat clinical laboratory sample must be collected and analyzed by the central laboratory and the event must be followed until resolution.	
Urine Pregnancy	
 • For all WOCBP: Test kit (dipsticks) provided by the central laboratory. The results of the urine dipstick test must be recorded in the source document and made available for study review. 	
Other Tests	
 • Follicle-stimulating hormone (only for post-menopausal status confirmation at screening) • Serum beta human chorionic gonadotropin (β-hCG) pregnancy test (for all WOCBP at screening, and for pregnancy status confirmation if urine dipstick pregnancy test is positive or if a urine dipstick test cannot be confirmed as negative [eg, an ambiguous result]) 	

Investigators must document their review of each laboratory safety report.

Table 8. Maximum Blood Volume by Test Parameter

Test Parameter	Volume (mL)
Serum Pregnancy Test (β -hCG), if applicable	1.1
Hematology	1.2
Serum Chemistry	1.1
Follicle-Stimulating Hormone, if applicable	2.0

10.3. Appendix 3: Adverse Events: Definitions and Procedures for Recording, Evaluating, Follow-up, and Reporting

10.3.1. Definition of AE

AE Definition

• An AE is any untoward medical occurrence in a patient or clinical study participant, temporally associated with the use of study intervention, whether or not considered related to the study intervention.• NOTE: An AE can therefore be any unfavorable and unintended sign (including an abnormal laboratory finding), symptom, or disease (new or exacerbated) temporally associated with the use of study intervention.
Events Meeting the AE Definition

• Any abnormal laboratory test results (hematology, clinical chemistry, or urinalysis) or other safety assessments (eg, electrocardiogram, radiological scans, vital signs measurements), including those that worsen from baseline, considered clinically significant in the medical and scientific judgment of the investigator (ie, not related to progression of underlying disease).• Exacerbation of a chronic or intermittent pre-existing condition including either an increase in frequency and/or intensity of the condition.• New conditions detected or diagnosed after study intervention administration even though it may have been present before the start of the study.• Signs, symptoms, or the clinical sequelae of a suspected drug-drug interaction.• Signs, symptoms, or the clinical sequelae of a suspected overdose of either study intervention or a concomitant medication. Overdose per se will not be reported as an AE/SAE unless it is an intentional overdose taken with possible suicidal/self-harming intent. Such overdoses should be reported regardless of sequelae.• “Lack of efficacy” or “failure of expected pharmacological action” per se will not be reported as an AE or SAE. Such instances will be captured in the efficacy assessments. However, the signs, symptoms, and/or clinical sequelae resulting from lack of efficacy will be reported as AE or SAE if they fulfil the definition of an AE or SAE.• The signs, symptoms, and/or clinical sequelae resulting from lack of efficacy will be reported as AE or SAE if they fulfil the definition of an AE or SAE. Also, “lack of efficacy” or “failure of expected pharmacological action” also constitutes an AE or SAE.

Events NOT Meeting the AE Definition

- Any clinically significant abnormal laboratory findings or other abnormal safety assessments which are associated with the underlying disease, unless judged by the investigator to be more severe than expected for the participant's condition.
- The disease/disorder being studied or expected progression, signs, or symptoms of the disease/disorder being studied, unless more severe than expected for the participant's condition.
- Medical or surgical procedure (eg, endoscopy, appendectomy): the condition that leads to the procedure is the AE.
- Situations in which an untoward medical occurrence did not occur (social and/or convenience admission to a hospital).
- Anticipated day-to-day fluctuations of pre-existing disease(s) or condition(s) present or detected at the start of the study that do not worsen.

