3. OBJECTIVES, ESTIMANDS AND ENDPOINTS

Objectives	Endpoints
Primary	

Efficacy: To evaluate the long-term efficacy of crisaborole ointment, 2%, QD for maintenance therapy and flare reduction in pediatric and adult participants ≥ 3 months of age with mild-to-moderate AD who responded to crisaborole ointment, 2%, BID treatment.	
Flare-free maintenance until onset of first flare during the 52-week double-blind period

Safety: To evaluate the safety and local tolerability of crisaborole ointment, 2%, QD for maintenance therapy and flare reduction in pediatric and adult participants ≥ 3 months of age with mild-to-moderate AD	
Incidence of treatment emergent adverse events
Secondary	

To evaluate other long-term efficacy parameters for maintenance therapy and flare reduction of crisaborole ointment, 2%, QD in pediatric and adult participants ≥ 3 months of age	Key secondary endpoints during the 52-week double-blind period: 
Number of flare-free daysNumber of flares

with mild-to-moderate AD who responded to crisaborole ointment, 2%, BID treatment
	
 • Pruritus response maintenance until onset of first flare 
Other secondary endpoints during the 52-week double-blind period:
 
 • $\geq 50\%$ reduction in Eczema Area and Severity Index (EASI)50 response maintenance • Maintenance of Dermatology Quality of Life Assessments • Maintenance of Patient Oriented Eczema Measure (POEM) 
The following will be assessed during flare treatment period:
 
 • Severity of flare on Investigator’s Static Global Assessment (ISGA) and EASI • Duration of flare episode

Additional Secondary
	

 • To evaluate the long-term efficacy of crisaborole ointment, 2%, QD for maintenance therapy and flare reduction in participants ≥ 3 months of age with mild-to-moderate AD 	
The following will be assessed as change from baseline of each respective treatment period (run-in, double-blind, and flare treatment):
 
 • EASI scores • ISGA scores • Treatable AD %BSA • Most commonly affected AD %BSA

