8.3. Adverse Events and Serious Adverse Events

The definitions of an AE or SAE can be found in [Appendix 3](#). For AD-related AEs, see [Section 8.3.6](#).

AE will be reported by the participant (or, when appropriate, by a caregiver, surrogate, or the participant's legally authorized representative).

The investigator and any qualified designees are responsible for detecting, documenting, and recording events that meet the definition of an AE or SAE and remain responsible to pursue and obtain adequate information both to determine the outcome and to assess whether it meets the criteria for classification as an SAE, or that caused the participant to discontinue the study intervention/study (see [Section 7](#)).

In addition, the investigator may be requested by Pfizer Safety to obtain specific follow-up information in an expedited fashion.

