8.3.6. Disease-Related Events and/or Disease-Related Outcomes Not Qualifying as AEs

The following disease related events are common in participants with AD:

- AD
- Eczema
- Flare of AD

Because these events are expected in this remitting and relapsing disease, they will not be reported as AEs. These events should be documented and recorded on the appropriate CRF as occurrence of a flare of AD during the maintenance period represents the efficacy outcome measure.

NOTE: However, if either of the following conditions applies, then the event must be recorded and reported as an AE:

- In the investigator's opinion, the event is of greater intensity or severity than the individual participant's condition at baseline (Day 1 of the run-in period).

OR

- The investigator considers that there is a reasonable possibility that the event was related to study intervention.

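### Protocol 10.3.1 gives opposite rules on whether lack of efficacy is an adverse event, so the TEAE count in the once-daily period can depend on which rule a site follows

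*Protocol*

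**What the plan says.** Protocol Section 10.3.1 addresses lack of efficacy twice, in neighbouring bullets of the list of events that meet the AE definition. The first says that lack of efficacy, or failure of the expected pharmacological action, "per se will not be reported as an AE or SAE. Such instances will be captured in the efficacy assessments". It adds that resulting signs and symptoms are reported if they meet the definition in their own right. The next bullet repeats that addition and then says that lack of efficacy "also constitutes an AE or SAE", without condition. The list of events that do not meet the definition includes "The disease/disorder being studied or expected progression, signs, or symptoms of the disease/disorder being studied, unless more severe than expected".

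Section 8.3 sends the reader to Appendix 3 for the AE and SAE definitions, then adds "For AD-related AEs, see" Section 8.3.6. That section names AD, eczema and flare of AD and says: "Because these events are expected in this remitting and relapsing disease, they will not be reported as AEs". It has two exceptions: the event is worse than the participant's condition on Day 1 of the run-in, or "The investigator considers that there is a reasonable possibility that the event was related to study intervention".

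The primary safety endpoint in Protocol Section 3 is "Incidence of treatment emergent adverse events". SAP Section 3.6.1 defines such an event by its start date only. SAP Section 6.7.1 summarises events separately for the open-label, once-daily (QD) and flare treatment periods. Protocol Section 9.4.2 makes the summary descriptive.

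**The concern.** The two bullets give opposite instructions for the same observation. One site may record lack of efficacy as an AE and another may not, and both can cite the protocol. No later step removes the difference, because the SAP definition does not filter by term.

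Two things are at stake. The first is the TEAE count itself. In a vehicle-controlled maintenance trial, lack of efficacy is expected more often on vehicle, so inconsistent recording need not balance out between arms. It could make crisaborole look better tolerated for a reason unrelated to tolerability. The second is SAE status: under Section 10.3.2 an event that is not an AE cannot be an SAE, whatever its consequences. The two bullets therefore also disagree on whether such an event can enter the 24-hour reporting in Section 8.3.1.1.

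**Working it through.** **1. The rules side by side**

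| Place | Lack of efficacy as a term | AD, eczema, flare of AD |
|---|---|---|
| 10.3.1, first bullet | Not an AE | Signs and symptoms only if they meet the definition |
| 10.3.1, next bullet | An AE or SAE | Same |
| 10.3.1, events not meeting the definition | Not named | Not an AE unless more severe than expected |
| 8.3.6 | Not named | Not an AE, with two exceptions |

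Section 8.3.6 settles most of the right-hand column. It does not settle the middle column, and no text ranks 8.3.6 against Appendix 3.

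**2. Where it can differ by arm**

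In the run-in everyone receives open-label crisaborole before randomization, so there is no arm comparison to distort. In flare treatment both arms receive open-label crisaborole BID, so failure there is not failure of vehicle. That leaves the QD-period summary.

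**3. The plan's own figure**

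Protocol Section 9.2 gives 162 first flares, hazard ratio 0.556, two-sided 0.05, 1:1 allocation and about 96% power. The Schoenfeld formula gives z = √162 × |ln 0.556| / 2 − 1.96 = 12.728 × 0.587 / 2 − 1.96 = 1.776, hence power 96.2%. The figure reproduces.

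**4. Flare proportions implied by that design (derived; the documents do not state them)**

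Take 125 per arm, 162 events in total and proportional hazards. Then p_v + p_c = 162/125 = 1.296 and 1 − p_c = (1 − p_v)^0.556. The solution is p_v = 75.4% (94.3 of 125) and p_c = 54.2% (67.7 of 125), a gap of 21.25 points.

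**5. Illustrative shift in TEAE incidence**

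Let b be the background TEAE incidence, equal in both arms, and q the share of flaring participants whose flare is recorded as an AE because of the second bullet. Assume that recording is independent of other events and that the event is counted in the QD period. Incidence in an arm is 1 − (1 − b)(1 − q·p), so vehicle minus crisaborole is (1 − b) × q × (p_v − p_c). The documents give neither b nor q.

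| q | b = 20% | b = 40% | b = 60% |
|---|---|---|---|
| 0 | 0 | 0 | 0 |
| 10% | 1.7 | 1.3 | 0.9 |
| 25% | 4.3 | 3.2 | 2.1 |

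Entries are percentage points. For example, 0.8 × 0.25 × 21.25 = 4.25 (shown as 4.3) and 0.4 × 0.10 × 21.25 = 0.85 (shown as 0.9).

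**The case against.** The strongest reply is that Section 8.3 already routes AD-related events to Section 8.3.6, and 8.3.6 keeps ordinary flares off the AE record. In this trial lack of efficacy shows mainly as AD worsening or flare, so a site that follows the pointer records little or nothing extra. The second bullet also repeats the first bullet's last sentence, which suggests a drafting slip rather than a deliberate rule. The analysis is descriptive, and SAP Section 6.7 already plans participant listings.

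Much of this stands. It limits the exposure mainly to sites that record lack of efficacy as its own term or let Appendix 3 override 8.3.6. It also means that applying q to all first flares is a device for showing scale, not a forecast. It does not remove the contradiction: 8.3.6 is silent on the term the second bullet makes reportable, and no order of precedence is given.

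Nor would reconciling the bullets remove every AD term from the AE tables. The two exceptions in 8.3.6 remain, and so does the bullet in 10.3.1 on exacerbation of a pre-existing condition. Some imbalance in AD terms between arms could legitimately remain.

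**Conclusion.** The contradiction is in the current text and should be resolved. It can change the primary safety count in the QD period and the SAE status of the events concerned. The illustrative shift is about 0.9 to 4.3 points of TEAE incidence, vehicle above crisaborole. It rests on the design's hazard ratio being true, on the derived 75% and 54%, and on the assumed ranges of q (10% to 25%) and b (20% to 60%). It is zero if no site applies the second bullet. No test or alpha is affected.

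A reader might go further and infer that the safety comparison is loaded against vehicle. The documents do not support that as a fact: it requires sites to apply the second bullet, to apply it despite 8.3.6, and vehicle to flare more. If every first flare were recorded, the same formula would give 8.5 to 17.0 points, but that supposes that 8.3.6 is ignored throughout. A reader might also compare the shift with the application site pain difference in Protocol Section 2.3 and infer that a tolerability signal could be hidden. That is not like for like. The figure concerns one treatment-related event in earlier studies, and recording lack of efficacy does not alter the count of that event.

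**What to change.** Reconcile the two bullets of Protocol Section 10.3.1 with each other and with Section 8.3.6, and state which section governs when they differ. Say explicitly how lack of efficacy recorded as a term of its own is to be handled, and notify sites.

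In the SAP, tabulate QD-period TEAEs by arm with and without lack-of-efficacy, Dermatitis atopic and Eczema terms. This also covers events already recorded, which a change to the protocol text alone would not reach. SAP Section 6.1.2 uses the last two as preferred terms to identify AD worsening, so the SAP should also say which record they come from.

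The cost is a clarifying change to the protocol text, with IRB/IEC handling if it is made as an amendment, a notice to sites and one extra table. No additional data collection is needed.
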